7.1 Procedures/Evaluations

Practice sites will be randomized using variable block sizes of 4 and 6 to ensure balance, with an even randomization ratio that will result in half of the sites randomized to the BE-EHR module activation (BE-EHR) and half randomized to usual care (UC). Randomization will be stratified by practice size (<= 100 patients vs > 100 patients over 75 with diabetes) to ensure balance. See Section 4.3 for greater detail.

Eligible patients from the chosen practice sites will be identified electronically within EPIC using an algorithm developed by the study team. This algorithm reviews patient records for diabetes codes in the Problem List. Patients 75 and over with one of the included codes are eligible. The algorithm is outlined below as well as a description of each component of the interventional module:

- 1. Evaluation of Choosing Wisely compliance using a built-in algorithm. The life expectancy algorithm was built into the BE-EHR module to drive timing and content of module firings that incorporate both patient life expectancy (high, medium, low) and target glycemic index per the CW guideline. These categories are defined as follows:
 - 1) healthy older adults with long life expectancy (>10 years): HbA1c target range of 7-7.5%
 - 2) those with moderate comorbidity and a moderate life expectancy (3-10 years): HbA1c target range of 7.5-8%
 - those with multiple comorbidities and shorter life expectancy (≤3 years): HbA1c target range of 8-9%
- 2. Firings of various module components using internal EPIC reporting. Each of the six components is triggered when a participant who has lower than recommended glycemic control is encountered in the system.
 - 1) Tailored Advisory: The Tailored Advisory nudge activates in Epic for any patient who is not CW compliant. For each patient seen, clinicians can respond by clicking the "Agree with

recommendation. Action taken" button, or by selecting the "Clinically inappropriate. Please explain" option, with space for free text comments. A response is not required.

- 2) Refill Protocol: The Refill Protocol nudge activates in Epic any time a medication refill for either Metformin or a non-Metformin diabetes medication is generated for a patient over 75
- 3) Preference List: The Preference List nudge is a system level nudge at the pilot sites. Metformin is listed at the top of the page as the choice for "First-line Type 2 Diabetes," without restricting orders for non-Metformin medications.
- Lab Result: The Lab Result nudge activates in Epic whenever there is a new A1c lab result for a non-CW compliant patient; the alert remains active in Epic for seven days following the result.
- 5) Peer Comparison: The Peer Comparison nudge is sent via a secured Microsoft Outlook account once per month. The subject line of the email is "Message from the desk of Dr. [Insert Practice Director Name]" and the email content includes three graphics: a CW compliance rate for the individual provider, a CW compliance rate for the clinician's practice site, and a CW compliance rate across all NYU Langone practices. Depending on whether the clinician's CW compliance rate was above or below the rate of their respective practice, the provider receives either a "negative" or "positive" version of the email
- 6) Campaign: The campaign toolkit for dissemination includes three gameshow-themed animations (Price is Right, Jeopardy, and Who Wants to Be a Millionaire), as well as a flashcard deck that quizzes physicians on CW best practices. The Price is Right campaign includes three unique variations and the Jeopardy campaign includes four unique variations.

7.2 Laboratory Procedures/Evaluations

Not applicable.

7.3 Study Specific Biospecimens

7.3.1 Specimen Collection Procedures

Not applicable.

7.3.2 Specimen Preparation, Handling, and Storage

Not applicable.

7.3.3 Specimen Shipment

Not applicable.

7.4 Questionnaire Administration

Not applicable.

8 Safety and Adverse Events

8.1 Definitions

Unanticipated Problems Involving Risk to Subjects or Others

Any incident, experience, or outcome that meets all of the following criteria:

- Unexpected in nature, severity, or frequency (i.e., not described in study-related documents such as the IRB-approved protocol or consent form, the investigators brochure, etc)
- Related or possibly related to participation in the research (i.e., possibly related means there is a reasonable possibility that the incident experience, or outcome may have been caused by the procedures involved in the research)

CONFIDENTIAL

Suggests that the research places subjects or others at greater risk of harm (including physical, psychological, economic, or social harm).

Adverse Event

An *adverse event* (AE) is any symptom, sign, illness or experience that develops or worsens in severity during the course of the study. Intercurrent illnesses or injuries should be regarded as adverse events. Abnormal results of diagnostic procedures are considered to be adverse events if the abnormality:

- results in study withdrawal
- is associated with a serious adverse event
- is associated with clinical signs or symptoms
- · leads to additional treatment or to further diagnostic tests
- is considered by the investigator to be of clinical significance

Serious Adverse Event

Adverse events are classified as serious or non-serious. A serious adverse event is any AE that is:

- fatal
- life-threatening
- requires or prolongs hospital stay
- results in persistent or significant disability or incapacity
- a congenital anomaly or birth defect
- an important medical event

Important medical events are those that may not be immediately life threatening, but are clearly of major clinical significance. They may jeopardize the subject, and may require intervention to prevent one of the other serious outcomes noted above. For example, drug overdose or abuse, a seizure that did not result in in-patient hospitalization, or intensive treatment of bronchospasm in an emergency department would typically be considered serious.

All adverse events that do not meet any of the criteria for serious should be regarded as *non-serious adverse events*.

Post-study Adverse Event

All unresolved adverse events should be followed by the investigator until the events are resolved, the subject is lost to follow-up, or the adverse event is otherwise explained. At the last scheduled visit, the investigator should instruct each subject to report any subsequent event(s) that the subject, or the subject's personal physician, believes might reasonably be related to participation in this study. The investigator should notify the study sponsor of any death or adverse event occurring at any time after a subject has discontinued or terminated study participation that may reasonably be related to this study.

8.2 Recording of Adverse Events

At each contact with the subject, the investigator must seek information on adverse events by specific questioning and, as appropriate, by examination. Information on all adverse events should be recorded immediately in the source document, and also in the appropriate adverse event module of the case report form (CRF). All clearly related signs, symptoms, and abnormal diagnostic procedures results should recorded in the source document, though should be grouped under one diagnosis.

All adverse events occurring during the study period must be recorded. The clinical course of each event should be followed until resolution, stabilization, or until it has been determined that the study treatment or participation is not the cause. Serious adverse events that are still ongoing at the end of the study period must be followed up to determine the final outcome. Any serious adverse event that occurs after the study period and is considered to be possibly related to study participation should be recorded and reported immediately.

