5.4 Strategies for Recruitment and Retention

Eligible patients from the chosen practice sites will be identified electronically within EPIC using an algorithm developed by the study team. This algorithm reviews patient records for diabetes codes in the Problem List. Patients 75 and over with one of the included codes are eligible. The algorithm then identifies their life expectancy category using comorbidity codes and assigns them to one of the three Choosing Wisely categories described in Section 4.2. Patients meeting eligibility will be automatically included, and all data collection will take place passively via the NYULH EHR system, EPIC. An EPIC reporting analyst will extract the relevant parameters from EPIC into a report. No study-specific case report forms will be used; rather, information from the patient's problem list, prescription history, and

CONFIDENTIAL

demographics will be used to compute compliance with CW guidelines. Patients from the selected practice sites will undergo their usual interactions with their providers and no study-specific activities will take place.

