5.7.3 Premature Termination or Suspension of Study

This study may be temporarily suspended or prematurely terminated if there is sufficient reasonable cause. Written notification, documenting the reason for study suspension or termination, will be provided by the suspending or terminating party to [name], the NIH/NIA, and regulatory authorities. If the study is prematurely terminated or suspended, the PI will promptly inform the IRB and will provide the reason(s) for the termination or suspension.

Circumstances that may warrant termination or suspension include, but are not limited to:

- Determination of unexpected, significant, or unacceptable risk to participants
- Insufficient compliance to protocol requirements
- Data that are not sufficiently complete and/or evaluable
- Determination of futility

Study activities may resume once concerns about safety, protocol compliance, and data quality are addressed and satisfy the sponsor and/or IRB.

6 Study Schedule

Participants will be included in this study by virtue of meeting eligibility criteria and having a patient encounter during the study period (i.e. the trial) of eighteen months from the date of randomization. There are no study-specific visits. Any patient meeting criteria who has one or more patient encounters during the 18-month study period will be included. Therefore, no study-specific visits are relevant for this study, so there is no schedule of visits.

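### Sections 8.1 and 8.2 prescribe adverse event steps that a passive EHR trial without case report forms or study visits cannot carry out, and the protocol describes no extraction of serious events for the review promised in Section 9

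*Combined protocol and SAP*

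**What the plan says.** Section 8.2 sets the method of ascertainment: "At each contact with the subject, the investigator must seek information on adverse events by specific questioning and, as appropriate, by examination". It sets the scope: "All adverse events occurring during the study period must be recorded". It also sets the place of recording: information should be "recorded immediately in the source document, and also in the appropriate adverse event module of the case report form (CRF"). Section 8.1, on events after the study, adds: "At the last scheduled visit, the investigator should instruct each subject to report any subsequent event(s").

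Section 9 makes the principal investigator responsible for safety oversight. It calls for a site data and safety-monitoring plan, and it promises a periodic review of the count and kind of serious adverse events. Section 15.1 has the principal investigator meet a Safety Officer once a year or more often.

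Elsewhere the protocol describes a passive trial. Section 5.4 says "No study-specific case report forms will be used" and that "no study-specific activities will take place"; Section 11 repeats that there are no such forms. Section 6 says "There are no study-specific visits", and Section 6.4 marks the final visit as not applicable. Under Section 12.3 consent is to be waived and patients are told nothing extra. Section 7 lists what the algorithm reads in order to judge compliance: demographics, problem-list diagnoses, prescriptions and laboratory results. It then says that the study team sees only the resulting classification.

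**The concern.** The safety sections read as if written for a trial that sees its participants, while the rest of the protocol describes one that does not. Two consequences follow. First, staff are given steps that they have no means of performing. Second, the serious-event review in Section 9 has no described input, so neither the principal investigator nor the Safety Officer can tell from the protocol what they would be reviewing.

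What is at stake is oversight. The Protocol Summary says that the module generally moves care toward less aggressive HbA1c targets and fewer medications other than metformin, in people aged 75 or older. If the trial commits itself to reviewing serious events in that population, the data for the review should be specified.

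**Working it through.** No formula applies to the main point; the check is a comparison of sections.

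| Step required | Where | What the rest of the protocol provides |
|---|---|---|
| Questioning and examination at each contact | 8.2 | No study-specific activities (5.4) or visits (6); patients have only their usual interactions with their own clinicians (5.4) |
| Entry in an adverse event module of a case report form | 8.2 | No study-specific forms (5.4, 11) |
| Entry in a source document | 8.2 | Possible: Section 11 counts clinical charts as source documents and makes Epic the primary data instrument |
| Instruction at a last scheduled visit | 8.1 | No visit schedule (6), final visit not applicable (6.4), no extra information to patients (12.3) |
| Periodic review of number and type of serious events | 9 | No extraction described |

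Of the four steps in Sections 8.1 and 8.2, only the source-document entry has a workable route.

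For the last row, I followed each place where a source might be named.

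1. Section 7. The listed fields are there to establish compliance and include no admissions, emergency visits or deaths. Problem-list diagnoses might show some events incidentally, but they are not described as a safety source. Taken literally, the closing sentence limits the study team to a two-valued result, from which serious events can be neither counted nor typed.
2. Section 12.3.3. Epic reports are mentioned, but not their content.
3. Section 8.3. Individual reports are required when an event is related, unexpected, and serious or a risk to others. That is a reporting duty for selected events, not a count of all serious events.
4. Section 9's cross-reference. It cites Section 11 under a title about auditing, monitoring and inspection. The actual Section 11 concerns source documents and access to them. It does allow monitoring and audit, but describes no flow of serious-event data.
5. Documents outside the protocol. Section 9 calls for a monitoring plan, Section 13.3 refers to a manual of procedures, and Section 18 says that attachments are held separately. None can be inspected here.

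One small figure helps with timing. The study period is 18 months and the minimum meeting frequency is yearly: 18 / 12 = 1.5, so one Safety Officer meeting within the period is guaranteed. More may be held, but no section says what serious-event data any of them would receive.

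**The case against.** The strongest reply is that this is generic safety wording in a trial that Section 2.3.1 rates as minimal risk. Section 12.3 equates the risks with those of standard care and leaves clinicians' autonomy intact, the endpoints are compliance and prescribing, and no between-arm safety claim is planned. Events are charted in Epic in any case, and a monitoring plan or manual may already say how serious ones are retrieved. The Section 7 list exists to determine compliance, so its omissions say little about safety reporting.

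Much of this stands. Minimal risk could justify light collection, but the text in force does not adopt that position: it requires all events to be recorded and promises a review. The unseen documents may supply a source, so the claim about Section 9 must be limited to what this protocol describes. They cannot, however, create a form module or a last visit in a trial that has neither.

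A reader might infer that the protocol as written would yield only spontaneously reported events. The documents do not support that: Section 8.2 also calls for source-document recording, charted events sit in Epic, and a separate plan may arrange retrieval.

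A reader might also combine the statement in Section 8.1 that "Intercurrent illnesses or injuries should be regarded as adverse events" with the broad definition of a deviation in Section 13.3, and conclude that every illness not entered on a form is a deviation. That is too formal. The sentence requiring all events to be recorded names no form, and an illness charted in Epic is arguably recorded.

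**Conclusion.** The point holds as an internal contradiction with a practical consequence. Contact-based questioning, form entry and last-visit instruction cannot be carried out as written, and the protocol describes no extraction of serious events for the review in Section 9. The wording conflict is certain from the text. The missing source is certain only for this protocol, because a monitoring plan or manual may name one.

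The primary analysis is not affected, and no numerical bias follows. It is tempting to size the problem by multiplying about 5000 patients by 1.5 years to get 7500 patient-years. That product is only a ceiling on exposure, since Section 6 admits a patient at any encounter during the 18 months, and it measures neither missed events nor harm.

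The conclusion rests on two readings: that treating clinicians are not acting as study investigators when they see patients, and that the Section 7 limit on what the team receives means what it says. If that limit was meant only for compliance data, the safety data flow is still not described.

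**What to change.** Reconcile Sections 8.1, 8.2 and 9 with Sections 5.4, 6, 7 and 11:

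- Replace the contact, form and last-visit wording with a passive Epic extract of serious events for all eligible patients in both arms, for example deaths, admissions and emergency visits.
- Amend the Section 7 sentence on what the study team receives so that this summary can be released.
- Supply the summary to the Safety Officer before each meeting under Section 15.1, and report it descriptively by arm.
- Correct Section 9's reference to Section 11, or cite the monitoring plan or manual of procedures if it already names the source.

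The cost is a protocol amendment, one added Epic report, a change to what the study team may receive and possibly an extension of the HIPAA waiver request. The extract would miss events treated outside the health system, and the report should say so. Randomization, endpoints and the primary model do not change.

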8.3 Reporting of Serious Adverse Events and Unanticipated Problems

Serious adverse events and unanticipated problems must be reported if they are:

- related to study participation,
- unexpected, and

•

• serious or involve risks to subjects or others.

For Narrative Reports of Safety Events

If the report is supplied as a narrative, the minimum necessary information to be provided at the time of the initial report includes:

- Study identifier
- Study Center
 - Subject number
- A description of the event
- Date of onset

- Current status
- Whether study treatment was discontinued
- The reason why the event is classified as serious
- Investigator assessment of the association between the event and study treatment

8.3.1 Investigator reporting: notifying the IRB

Federal regulations require timely reporting by investigators to their local IRB of unanticipated problems posing risks to subjects or others. The following describes the NYULMC IRB reporting requirements, though Investigators at participating sites are responsible for meeting the specific requirements of their IRB of record.

Report Promptly, but no later than 5 working days:

Researchers are required to submit reports of the following problems promptly but no later than 5 working days from the time the investigator becomes aware of the event:

- Unanticipated problems including adverse events that are unexpected and related
 - Unexpected: An event is "unexpected" when its specificity and severity are not accurately reflected in the protocol-related documents, such as the IRB-approved research protocol, any applicable investigator brochure, and the current IRB-approved informed consent document and other relevant sources of information, such as product labeling and package inserts.
 - Related to the research procedures: An event is related to the research procedures if in the opinion of the principal investigator or sponsor, the event was more likely than not to be caused by the research procedures.
 - Harmful: either caused harm to subjects or others, or placed them at increased risk

Other Reportable events:

The following events also require prompt reporting to the IRB, though *no later than 5 working days*:

- **Complaint of a research subject** when the complaint indicates unexpected risks or the complaint cannot be resolved by the research team.
- **Protocol deviations or violations** (includes intentional and accidental/unintentional deviations from the IRB approved protocol) for any of the following situations:
 - one or more participants were placed at increased risk of harm
 - the event has the potential to occur again
 - the deviation was necessary to protect a subject from immediate harm
- Breach of confidentiality
- Incarceration of a participant when the research was not previously approved under Subpart C and the investigator believes it is in the best interest of the subject to remain on the study.
- New Information indicating a change to the risks or potential benefits of the research, in terms of severity or frequency. (e.g. analysis indicates lower-than-expected response rate or a

CONFIDENTIAL

more severe or frequent side effect; Other research finds arm of study has no therapeutic value; FDA labeling change or withdrawal from market)

Reporting Process

The reportable events noted above will be reported to the IRB using a Reportable New Information submission and will include a description of the event with information regarding its fulfillment of the above criteria, follow-up/resolution, and need for revision to consent form and/or other study documentation. Copies of each report and documentation of IRB notification and receipt will be kept in the Clinical Investigator's study file.

9 Study Oversight

It is the responsibility of the Principal Investigator to oversee the safety of the study at her site. This safety monitoring will include careful assessment and appropriate reporting of adverse events as noted above, as well as the construction and implementation of a site data and safety-monitoring plan (see Section 11: Study Auditing, Monitoring and Inspecting). Medical monitoring will include a regular assessment of the number and type of serious adverse events.

10 Statistical Considerations

10.1 Study Hypotheses

Patient in clinics receiving the BE-EHR module will have higher rates of CW compliance.

10.2 Sample Size Determination

Our preliminary data indicate that approximately 30-40% of eligible patients have care that is CWcompliant. We wish to be able to detect an increase in the rate of CW-compliant care of ten percentage points or more. We conservatively estimate an ICC (intra-class correlation coefficient, a measure of the degree of additional correlation among providers within the same practice) of 0.05; with an average of four providers per practice site at 70 sites, this leads to a design effect of 1.15. The sample of 280 providers becomes an effective sample size of 244, providing approximately 87% power to detect a difference of ten percentage points between the study arms.

